5.4.3 Reporting Requirements for Pregnancies

5.4.3.1 Pregnancies in Female Patients

Female patients of childbearing potential will be instructed to immediately inform the investigator if they become pregnant during the study or within 60 days after the final dose of study drug. A paper Clinical Trial Pregnancy Reporting Form should be completed and submitted to the Sponsor or its designee immediately (i.e., no more than 24 hours after learning of the pregnancy), either by faxing or by scanning and emailing the form using the fax number or email address provided to investigators. Pregnancy should not be recorded on the Adverse Event eCRF. The investigator should discontinue study drug and counsel the patient, discussing the risks of the pregnancy and the possible effects on the fetus. Monitoring of the patient should continue until conclusion of the pregnancy. Any serious adverse events associated with the pregnancy (e.g., an event in the fetus, an event in the mother during or after the pregnancy, or a congenital anomaly/birth defect in the child) should be reported on the Adverse Event eCRF. In addition, the investigator will submit a Clinical Trial Pregnancy Reporting Form when updated information on the course and outcome of the pregnancy becomes available.

5.4.3.2 Pregnancies in Female Partners of Male Patients

Male patients will be instructed through the Informed Consent Form to immediately inform the investigator if their partner becomes pregnant during the study or within 60 days after the final dose of study drug. A paper Clinical Trial Pregnancy Reporting Form should be completed and submitted to the Sponsor or its designee immediately (i.e., no more than 24 hours after learning of the pregnancy), either by faxing or by scanning and emailing the form using the fax number or email address provided to investigators. Attempts should be made to collect and report details of the course and outcome of any pregnancy in the partner of a male patient exposed to study drug. When permitted by the site, the pregnant partner would need to sign an Authorization for Use and Disclosure of Pregnancy Health Information to allow for follow-up on her pregnancy. If the authorization has been signed, the investigator should submit a Clinical Trial Pregnancy Reporting Form when updated information on the course and outcome of the pregnancy becomes available. An investigator who is contacted by the male patient or his pregnant partner may provide information on the risks of the pregnancy and the possible effects on the fetus, to support an informed decision in cooperation with the treating physician and/or obstetrician.

5.4.3.3 Abortions

A spontaneous abortion should be classified as a serious adverse event (as the Sponsor considers abortions to be medically significant), recorded on the Adverse Event eCRF, and reported to the Sponsor immediately (i.e., no more than 24 hours after learning of the event; see Section [5.4.2](#)).

If a therapeutic or elective abortion was performed because of an underlying maternal or embryofetal toxicity, the toxicity should be classified as a serious adverse event, recorded on the Adverse Event eCRF, and reported to the Sponsor immediately (i.e., no more than 24 hours after learning of the event; see Section [5.4.2](#)). A therapeutic or elective abortion performed for reasons other than an underlying maternal or embryofetal toxicity is not considered an adverse event.

All abortions should be reported as pregnancy outcomes on the paper Clinical Trial Pregnancy Reporting Form.

5.4.3.4 Congenital Anomalies/Birth Defects

Any congenital anomaly/birth defect in a child born to a female patient exposed to study drug or the female partner of a male patient exposed to study drug should be classified as a serious adverse event, recorded on the Adverse Event eCRF, and reported to the Sponsor immediately (i.e., no more than 24 hours after learning of the event; see Section [5.4.2](#)).

5.5 FOLLOW-UP OF PATIENTS AFTER ADVERSE EVENTS

5.5.1 Investigator Follow-Up

The investigator should follow each adverse event until the event has resolved to baseline grade or better, the event is assessed as stable by the investigator, the patient is lost to follow-up, or the patient withdraws consent. Every effort should be made to follow all serious adverse events considered to be related to study drug or trial-related procedures until a final outcome can be reported.

During the study period, resolution of adverse events (with dates) should be documented on the Adverse Event eCRF and in the patient's medical record to facilitate source data verification.

All pregnancies reported during the study should be followed until pregnancy outcome.

5.5.2 Sponsor Follow-Up

For serious adverse events, adverse events of special interest, and pregnancies, the Sponsor or a designee may follow up by telephone, fax, email, and/or a monitoring visit to obtain additional case details and outcome information (e.g., from hospital discharge summaries, consultant reports, autopsy reports) in order to perform an independent medical assessment of the reported case.

5.6 ADVERSE EVENTS THAT OCCUR AFTER THE ADVERSE EVENT REPORTING PERIOD

The Sponsor should be notified if the investigator becomes aware of any serious adverse event that occurs after the end of the adverse event reporting period (defined as 84 days after the final dose of study drug or end of study (Week 58) for patients who discontinue study drug but remain on study, or 6 weeks following the placebo dose for patients who failed to be randomized), if the event is believed to be related to prior study drug treatment. These events should be reported through use of the Adverse Event eCRF. However, if the EDC system is not available, the investigator should report these events directly to the Sponsor or its designee, either by faxing or by scanning and emailing the paper Clinical Trial Serious Adverse Event/Adverse Event of Special Interest Reporting Form using the fax number or email address provided to investigators.

5.7 EXPEDITED REPORTING TO HEALTH AUTHORITIES, INVESTIGATORS, INSTITUTIONAL REVIEW BOARDS, AND ETHICS COMMITTEES

The Sponsor will promptly evaluate all serious adverse events and adverse events of special interest against cumulative product experience to identify and expeditiously communicate possible new safety findings to investigators, IRBs, ECs, and applicable health authorities based on applicable legislation.

To determine reporting requirements for single adverse event cases, the Sponsor will assess the expectedness of these events using the following reference document:

- MTPS9579A Investigator's Brochure

The Sponsor will compare the severity of each event and the cumulative event frequency reported for the study with the severity and frequency reported in the applicable reference document.

Reporting requirements will also be based on the investigator's assessment of causality and seriousness, with allowance for upgrading by the Sponsor as needed.

An IMC will monitor the incidence of the above-listed anticipated events during the study (see Section 3.1.3).

6. STATISTICAL CONSIDERATIONS AND ANALYSIS PLAN

The primary and secondary efficacy analyses will be based on a modified intent-to-treat (mITT) approach. All patients randomized who received at least one dose of study drug will be included in the mITT analysis set and be included in the analysis, with patients grouped according to the treatment assigned at randomization.

All safety analyses will include all randomized patients who received any study drug. For these analyses, patients will be grouped according to the treatment actually received.

An interim efficacy analysis is planned to be performed after approximately 51 patients have experienced a CompEx event in the 48-week, double-blind treatment period. For the interim analysis, the treatment assignments will be unblinded to relevant Sponsor study team members performing the analyses. The other parties who are involved in the conduct of the study (e.g., patients, site monitors, investigators) will remain blinded to patient-specific treatment assignments until the final database lock after the completion of the study.

The final analysis of data will be performed when all patients have either completed the study completion/early termination visit or discontinued early from the study. In addition, all data collected from the study will be cleaned, verified, and locked in a database.

All primary and secondary hypotheses tests will be two-sided with a type I error rate of 0.2. To aid the interpretation and understand the clinically significant differences from the formal hypothesis testing, two-sided 95% confidence intervals will be provided. There will be no adjustment made for any multiple comparisons. In addition, there will be no type I error control methods triggered as a result of the interim analysis.

Detailed specifications of all statistical methods (including scoring of PRO instruments and missing data handling) will be provided in the Data Analysis Plan (DAP).

6.1 DETERMINATION OF SAMPLE SIZE

The primary goal of this trial is estimation rather than hypothesis testing. This is largely due to the uncharacterized distribution of CompEx in the placebo arm. The interim analysis based upon 51 events will yield reasonable precision for estimating the true underlying hazard ratio. [REDACTED]

6.2 SUMMARIES OF CONDUCT OF STUDY

The number of patients who enroll, discontinue (early discontinuation of treatment or early termination from the study), or complete the study will be summarized. Reasons for early discontinuation of treatment or premature study withdrawal will be listed and summarized by treatment group. Enrollment and major protocol deviations will be listed and evaluated for their potential effects on the interpretation of study results. All summaries will be presented according to randomized treatment assignment.

6.3 SUMMARIES OF TREATMENT GROUP COMPARABILITY

Baseline demographics, disease characteristics, and exposure to study drug will be summarized overall and by treatment group using descriptive statistics. For categorical endpoints, the descriptive statistics will include counts and proportions. For continuous endpoints, the descriptive statistics will include the number of observations, mean, standard deviation, median, minimum, and maximum.

6.4 EFFICACY ANALYSES

Efficacy analyses will be conducted on an mITT population, consisting of all randomized patients who received at least one dose of study drug during the 48-week double-blind treatment period, with patients grouped according to the treatment assigned at randomization.

Unless otherwise noted, analyses of efficacy outcome measures will be adjusted by blood eosinophil level (Visit 1 < 150 cells/ μ L, 150–300 cells/ μ L, > 300 cells/ μ L) and geographic region (United States/Western Europe, Eastern Europe, Southern Hemisphere).

6.4.1 Primary Efficacy Endpoint

The primary efficacy endpoint is time to first CompEx event, defined as time from randomization to first asthma exacerbation or diary worsening during the 48-week double-blind treatment period. Asthma exacerbations and diary worsening are defined as follows:

- Asthma exacerbations are assessed by the investigator and defined as new or increased asthma symptoms (wheezing, coughing, dyspnea, chest tightness, and/or nighttime awakenings due to these symptoms) that result in one or both of the following:
 - Hospitalization or an emergency department or urgent care visit requiring administration of systemic corticosteroid treatment
 - Treatment with systemic (IV, IM, or oral) corticosteroids for \geq 3 days or a long-acting depot corticosteroid preparation with a therapeutic effectiveness of \geq 3 days
- Diary worsening is based on the occurrence of prespecified changes (deteriorations) in the following six parameters: morning PEFR, evening PEFR, morning symptom score, evening symptom score, morning short-acting rescue therapy use, and evening short-acting rescue therapy use. Deterioration criteria, defined as either a change from baseline (threshold) or worsening of a certain magnitude (slope) over 5 consecutive days, are presented for each parameter in [Appendix 8](#). Diary worsening is defined as occurrence of one or both of the following scenarios:

- Patient meets threshold deterioration criterion (i.e., prespecified change from baseline) for PEFR (morning and/or evening) and at least one other parameter (i.e., morning symptom score, evening symptom score, morning rescue therapy use, and/or evening rescue therapy use) on 2 consecutive days.
- Patient meets threshold deterioration criterion (i.e., prespecified change from baseline) for one parameter on 2 consecutive days and slope deterioration criterion (i.e., prespecified change over 5 consecutive days calculated via univariate linear regression) for all six parameters.

For the purposes of determining whether the threshold deterioration criteria are met, baseline levels are calculated for each individual as the mean over the 10 planned sessions conducted prior to time of randomization for each of the diary variables.

In the event that the first diary worsening scenario is met (i.e., threshold met in two parameters), the diary worsening event will start on the first of the 2 consecutive days (defined as Event Days 0 and 1).

In the event that the second diary worsening scenario is met (i.e., threshold in one parameter and slope in all six parameters), the diary worsening event will start on the first of the 2 consecutive days that the threshold was met (Event Days 0 and 1), and the slope criteria for the six parameters must be met on Day 0 and the 4 consecutive days prior to that day (i.e., Event Day –4 through Event Day 0).

To qualify for the second diary worsening scenario, data from at least 3 of the 5 consecutive days must be available for calculation of the slope for each parameter. Analyses will be based on observed asthma exacerbations and diary worsenings, with no imputation for premature discontinuation or missing diary entries.

The primary endpoint will be analyzed through use of a Cox proportional hazards regression model comparing MTPS9579A with placebo with respect to time to first CompEx event, with adjustment for baseline covariates as described in Section 6.4. Estimated hazard ratios and their associated 95% confidence intervals will be provided. Further details regarding the primary endpoint and the analysis will be described in the DAP.

6.4.2 Secondary Efficacy Endpoints

The secondary efficacy endpoints are as follows:

- Rate of asthma exacerbations (as defined in Section 2.1.1) during the 48-week double-blind treatment period
- Time to first asthma exacerbation during the 48-week double-blind treatment period
- Absolute and relative change from randomization in pre-bronchodilator FEV₁ (liters) at Week 50
- Absolute and relative change from randomization in FeNO at Week 50

The secondary endpoints will be evaluated in the mITT population. Statistical models will be adjusted for baseline covariates, as described in Section 6.4. The annualized exacerbation rate will be estimated for each arm as the total number of protocol-defined asthma exacerbations observed over the treatment period divided by total patient-years at risk. For each individual patient, years at risk will be computed as the number of days from the date of randomization to the date of treatment completion or discontinuation, divided by 365.25 days. Poisson regression with over-dispersion will be used in the analysis to assess the treatment effect on the rate of asthma exacerbations. Analyses will be based on observed exacerbations, with no imputation for premature discontinuation. In addition, a patient's time at risk, as defined above, will be computed and used as an offset term in the model.

Continuous endpoints will be analyzed using mixed-model repeated measures. Time-to-event endpoints will be analyzed using a Cox proportional hazards regression model. For the categorical variables, appropriate statistical methods, such as Cochran-Mantel-Haenszel test or Fisher's exact test, will be used. Descriptive summaries for continuous endpoints will include mean, standard deviation, median, and range. Descriptive summaries for categorical endpoints will include counts and proportions.

Descriptive summaries for continuous endpoints will include mean, standard deviation, median, and range. Descriptive summaries for categorical endpoints will include counts and proportions. Further details will be described in the DAP.

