2.1 EFFICACY OBJECTIVES

2.1.1 Primary Efficacy Objective

The primary efficacy objective for this study is to evaluate the efficacy of MTPS9579A compared with placebo on the basis of the following endpoint:

- Time to first CompEx event (Fuhlbrigge et al. 2017), a composite endpoint defined as time from randomization to first asthma exacerbation or diary worsening during the 48-week double-blind treatment period (from the randomization visit [Week 2] to end of treatment [Week 50]). Asthma exacerbations and diary worsening are defined as follows:

Asthma exacerbations are assessed by the investigator and defined as new or increased asthma symptoms (wheezing, coughing, dyspnea, chest tightness, and/or nighttime awakenings due to these symptoms) that result in one or both of the following:

- Hospitalization or an emergency department or urgent care visit requiring administration of systemic corticosteroid treatment
- Treatment with systemic (IV, intramuscular [IM], or oral) corticosteroids for ≥ 3 days or a long-acting depot corticosteroid preparation with a therapeutic effectiveness of ≥ 3 days
- Diary worsening is based on the occurrence of prespecified changes (deteriorations) in a subset of the following six parameters: morning peak expiratory flow rate (PEFR), evening PEFR, morning symptom score, evening symptom score, morning short-acting rescue therapy use, and evening short-acting rescue therapy use. A detailed definition of diary worsening is provided in Section 6.4.1.

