4.4 CONCOMITANT THERAPY AND ADDITIONAL RESTRICTIONS

Concomitant therapy consists of any medication (e.g., prescription drugs, over-the-counter drugs, vaccines, herbal or homeopathic remedies, nutritional supplements) used by a patient in addition to protocol-mandated treatment from 7 days prior to screening (for medications not intended for the treatment of asthma) or 3 months prior to screening (for medications intended for the treatment of asthma) to the study completion/discontinuation visit. All such medications should be reported to the investigator and recorded on the Concomitant Medications eCRF.

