Appendix 1: Schedule of Activities

ACQ-5=Asthma Control Questionnaire (5 items); ADA=anti-drug antibody; eDiary=electronic diary; EOT=end of treatment; ET=early termination; FeNO=fractional exhaled nitric oxide; PBO=placebo; PEFR=peak expiratory flow rate; PK=pharmacokinetic; PPD=purified protein derivative; Rand.=randomization; SNP=single nucleotide polymorphism; TB=tuberculosis; UV=unscheduled visit; WGS=whole genome sequencing.

Notes: On treatment days, all assessments should be performed prior to study drug dosing, unless otherwise specified.

- ^a The screening period may last up to 4 weeks. The earliest a patient can qualify for the run-in period is after 12 days, when eDiary compliance criteria are met. Patients are allowed one attempt to re-screen.
- ^b Run-in takes place from Day 1 through Day 14 to assess baseline eDiary symptoms; however, these assessments must be performed on Day 1 (± 2 days).
- ^c Note that these tests occur on the same day, before (left column) or after (right column) the patient has been randomized.
- ^d Patients who complete the treatment period will return to the clinic for a treatment completion visit at Week 50. Patients who discontinue study drug for any reason should continue follow-up for all remaining study visits through the end of the study.
- ^e Final safety follow-up will be conducted by telephone call.
- ^f Patients who experience symptoms consistent with an asthma exacerbation will be asked to come to the clinic for an unscheduled visit for additional evaluations. Assessments should be performed as clinically indicated.
- ^g Patients who are randomly allocated to the 48-week double-blind treatment period but discontinue study drug should continue follow-up for all other study procedures and measurements through the end of the study, except for collection of serum and nasosorption samples for biomarkers.
- ^h Informed consent must be documented before any study-specific screening procedure is performed.
- ⁱ Includes evaluation of the head, eyes, ears, nose, and throat, and the cardiovascular, dermatologic, musculoskeletal, respiratory, gastrointestinal, and neurologic systems.

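### The exacerbation rate is named over 48 weeks, but Section 6.4.2 most naturally ends time at risk when study drug stops; no common end date is stated

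*Protocol*

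**What the plan says.** Protocol Section 6.4.2 lists the endpoint as "Rate of asthma exacerbations (as defined in Section 2.1.1) during the 48-week double-blind treatment period". Section 2.1.1 fixes that period by calendar, the same for every patient: "48-week double-blind treatment period (from the randomization visit [Week 2] to end of treatment [Week 50".

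The annualized rate in each arm is the "total number of protocol-defined asthma exacerbations observed over the treatment period divided by total patient-years at risk". A patient's years at risk are the "number of days from the date of randomization to the date of treatment completion or discontinuation, divided by 365.25 days". The same quantity is the offset in the over-dispersed Poisson model. The section adds that observed exacerbations are used, without imputation for premature discontinuation.

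Appendix 1, footnote d, dates treatment completion: "Patients who complete the treatment period will return to the clinic for a treatment completion visit at Week 50". It continues: "Patients who discontinue study drug for any reason should continue follow-up for all remaining study visits through the end of the study". Section 4.6.1 also keeps patients who stop drug in follow-up to Week 58, and Section 4.5.12 has the investigator ask about exacerbations at each visit.

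SAP Output 3.3 is titled for the 48-week period. It has a row for total follow-up time at risk and a footnote naming the log of patient time at risk as the offset. It defines neither and has no rule for events after drug is stopped.

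**The concern.** A rate needs its events and its exposure taken from the same interval. Here the event window is a fixed 48 weeks, while the exposure window appears to close when the patient stops drug. A patient who stops early and has an exacerbation before Week 50 would add an event but not the time in which it occurred.

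This is the first-listed secondary endpoint, and Section 6.8 gives it as an example among the primary and key secondary endpoints. Section 6.1 says the trial's main goal is estimation, so a shifted ratio or a needlessly wide interval bears on what the trial is for.

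**Working it through.** **1. What does discontinuation mean in Section 6.4.2?** The protocol does not say. These points favor stopping study drug:
- The word is paired with treatment completion, which Appendix 1 ties to Week 50.
- Where leaving the study is meant, the protocol says so. Section 6 has "completed the study completion/early termination visit or discontinued early from the study" and Section 4.4 has "to the study completion/discontinuation visit".
- Sections 4.6.1 and 4.6.2 treat the two kinds of stopping separately. SAP Outputs 1.5 and 1.6 tabulate them separately, and Outputs 1.7 and 1.8 list them separately.

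These points favor leaving the study: Section 6.2 uses discontinue for both kinds, and the Output 3.3 row label speaks of follow-up time.

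**2. The four pairings**

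| Events counted | Time at risk ends at | Result |
|---|---|---|
| To Week 50, on or off drug | Study exit or Week 50 | Matched |
| On drug only | Drug stop | Matched, but not the named 48-week rate |
| To Week 50, on or off drug | Drug stop | Rates overstated |
| On drug only | Study exit or Week 50 | Rates understated |

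**3. Inputs.** From the documents: a 48-week window (48 × 7 = 336 days), a two-sided level of 0.2 (Section 6), and 69 active and 65 placebo mITT patients (SAP Output 1.1). The visible text gives no stopping, retention or event rate for this endpoint, so the rest is assumed:
- d = share stopping drug
- w = weeks on drug before stopping
- g = share of the remaining time to Week 50 that is observed
- the same event rate on and off drug

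**4. Bias, third pairing.** The factor by which an arm's rate is inflated is

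[(1−d)·48 + d·(w + g·(48−w))] / [(1−d)·48 + d·w]

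For w = 8 and g = 1:
- Active, d = 0.20: 48 / (38.4 + 1.6) = 1.200
- Placebo, d = 0.10: 48 / (43.2 + 0.8) = 1.091
- Null rate ratio: 1.200 / 1.091 = 1.100

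| Null ratio, 20% active vs 10% placebo | w = 8 | w = 16 | w = 24 |
|---|---|---|---|
| Full off-drug follow-up (g = 1) | 1.100 | 1.077 | 1.056 |
| Half (g = 0.5) | 1.052 | 1.040 | 1.028 |

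The fourth pairing gives the reciprocals: 0.909 to 0.947 (g = 1) and 0.950 to 0.972 (g = 0.5). Either matched pairing, g = 0, or equal amount and timing of stopping gives 1.000. Equal 15% stopping with unequal timing (8 weeks on drug in one arm, 24 in the other) gives 1.057 (g = 1).

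A gap in stopping can arise by chance. With 15% stopping in both arms, the SD of the difference is √[0.15 × 0.85 × (1/69 + 1/65)] = 0.0617. A gap of 10 points or more is then 0.10/0.0617 = 1.62 SD, two-sided probability 0.105.

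**5. Precision and test, third pairing.** Simulation of a Poisson model with Pearson scale, treatment term only, 69 and 65 patients. Unless stated otherwise: 1 event/year, over-dispersion 1.5, stopping spread over 4 to 44 weeks, full off-drug follow-up. Arrows run from the matched 48-week window to 48-week events over on-drug time. SE is that of the log rate ratio.

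| Scenario | Result |
|---|---|
| Null, 15% stopping in both arms | SE 0.221 → 0.250 (+13%); dispersion 1.48 → 1.92; rejection at 0.2: 0.198 → 0.155 |
| Same, half follow-up | SE 0.224 → 0.236 (+5%); rejection 0.199 → 0.181 |
| True ratio 0.60, 20% active vs 10% placebo | estimate 0.596 → 0.630; power 0.803 → 0.671 |
| True ratio 0.60, 10% active vs 20% placebo | estimate 0.594 → 0.563 |
| Null, 30% vs 10%, all stopping after 24 weeks, 1.5 events/year, no over-dispersion | rejection 0.29 on the mismatched analysis |

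Over event rates of 0.5 to 1.5/year, over-dispersion 1 to 2 and equal 10–15% stopping, the SE rises by 7–16% (full follow-up) or 3–7% (half).

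**The case against.** The strongest reply is that the text can be read so that the windows match. Discontinuation may mean leaving the study, as the Output 3.3 label suggests. Or the treatment period may be each patient's own: footnote d speaks of patients who complete it, which implies that some do not. The sentence ruling out imputation for premature discontinuation points the same way, since there is little to impute if off-drug events are observed and counted.

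These readings are possible, so the documents do not support saying outright that the windows conflict. But neither document adopts any of them. A per-patient treatment period sits badly with the calendar definition in Section 2.1.1. The no-imputation sentence does not exclude observed off-drug events, because using them is not imputation. Two programmers could derive different offsets from the same text.

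It is also fair to say that the size is hypothetical and moderate. At a standard error near 0.22, a null ratio of 1.06 to 1.10 is a shift of about a quarter to under half a standard error (ln 1.056/0.22 = 0.25; ln 1.100/0.22 = 0.43). The upper figure needs every patient who stops to do so after 8 weeks and be followed fully. The simulation also leaves out the planned covariates.

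**Conclusion.** The point stands as a defect in the stated rule, with medium confidence. On its most natural reading, Section 6.4.2 divides 48-week events by on-drug time. The text that would rule this out is absent from the protocol and from the SAP as published.

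On that reading, and under the assumptions above, arm rates are overstated whenever patients who stop drug are followed and have later events. The interval widens even when stopping is balanced. The rate ratio shifts in either direction if stopping differs between arms in amount or timing.

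Three stronger inferences are not supported:
- **That the ratio is biased in any case.** With equal amount and timing of stopping, and equal follow-up and off-drug event rates, it is not.
- **That the test rejects too often, or that it never does.** With equal stopping it is at or below nominal (0.10 to 0.20 at the 0.2 level). With very unequal stopping it can exceed nominal, as in the 0.29 case.
- **That the main result is affected.** The primary endpoint and time to first exacerbation do not use this offset.

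The change should be made, because the size cannot be bounded from the documents and the correction is cheap.

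**What to change.** In Section 6.4.2 and the Output 3.3 footnote, state: *Exacerbations with onset from randomization to the earlier of the scheduled Week 50 date (randomization + 336 days) and study exit are counted, whether or not the patient is still on study drug. Time at risk is that same interval divided by 365.25, and its log is the offset.*

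Use the scheduled date rather than the Week 50 visit. Otherwise a patient who misses that visit but stays in the study would contribute events and time beyond 48 weeks.

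A supportive on-treatment version may be added, with events and offset both cut at the same defined treatment-discontinuation date.

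The cost is one sentence in two places and one extra date derivation. No new data are needed: the protocol already requires the follow-up, and SAP Output 1.7 already lists the day of study discontinuation. The supportive version adds one model fit and one output.
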